5.0 Adverse Event Reporting

An Adverse Event is the development of an untoward medical occurrence or the deterioration of a pre-existing medical condition following or during exposure to an investigational product, whether or not considered causally related to the product or the surgical procedure to implant it. An untoward medical condition can be symptoms (e.g., nausea), signs (e.g., tachycardia, fever) or clinically significant abnormal results of an investigation (e.g., laboratory findings, chest x-ray).

Adverse events that occur during this study may be associated with the implant procedure, including those from general anesthesia, or specifically associated with the use of the device. An adverse event will be considered to be device-related when, in the judgment of the Primary Investigator, there is a logical connection between the use of the device and the occurrence of the event, above and beyond the study procedure itself. Adverse events will be counted regardless of severity, seriousness, onset, duration, or relation to study treatment. A serious adverse event (SAE) is any untoward medical occurrence which:

- Results in death;
- Is life-threatening;
- Requires in-patient hospitalization for > 24 hours or prolongation of hospitalization which is not specifically required by the protocol;
- Results in permanent impairment of a body function or permanent damage to a body structure; or
- Requires medical or surgical intervention to preclude permanent impairment of a body function or permanent damage to a body structure.

For any SAE, if the Primary Investigator judges that there is a logical connection (caused or contributed to) between the use of the device and the occurrence, the SAE will be noted as device-related.

All adverse event rates will be reported as the number and frequency of events with corresponding 95% exact binomial confidence limits, as well as the number of events per patient-time (e.g., events per 10 patient years). These values will be qualitatively compared to the same rates observed in previous cochlear implant studies; no formal statistical comparisons will be conducted.

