2.0 Clinical Study Design Overview

This clinical investigation will be conducted as a multicenter, prospective, nonrandomized, single-subject, repeated-measures design in which each subject serves as his/her own control. This approach accommodates the heterogeneity that characterizes hearing-impaired populations. Blinding procedures are not appropriate for this trial design, as it is not possible to conceal the presence, or absence, of a cochlear implant (CI) system from recipients and/or clinical Investigators.

Subjects in this study will be implanted with the commercially available Nucleus CI532 cochlear implant and fit with the CP1000/Nucleus 7 Sound Processor. All testing will be complete with CP1000/Nucleus 7 Sound Processor.

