- A significance level of $\alpha = 0.05$ (two-tailed).
- A desired power of 0.9

Based on these assumptions, a sample size of 26 subjects is required to achieve a power of 90%.

A sample size of 100 adult subjects will be enrolled in the clinical investigation, this large sample will allow for additional analyses to be conducted specifically the additional patient reported outcome measures, where a large sample size is typically desired. Additionally the sample size provides greater justification for generalizability to the wider clinical population.

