4.2 Study Population

All subjects who are consented and enrolled into the clinical study will constitute the intention-to-treat (ITT) population for the purposes of adverse event reporting. Only subjects implanted with the CI532 and fit with the CP1000/N7 Sound Processor and completed per the protocol will be considered as the completed cases (CC) population and per protocol (PP).

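### Exact binomial limits are attached to adverse event counts, and the adverse event population includes enrolled subjects who may never be exposed; limits and rates are unreliable if events recur or surgery does not happen

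*SAP*

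**What the plan says.** SAP section 5.0 sets the reporting rule: "All adverse event rates will be reported as the number and frequency of events with corresponding 95% exact binomial confidence limits", and the same sentence adds "as well as the number of events per patient-time (e.g., events per 10 patient years"). It names no interval method for the patient-time rate and no start for time at risk.

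The counting rule in section 5.0 is inclusive: "Adverse events will be counted regardless of severity, seriousness, onset, duration, or relation to study treatment". There is no rule of one event per subject. An adverse event is defined there as an occurrence "following or during exposure to an investigational product, whether or not considered causally related to the product or the surgical procedure to implant it".

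Section 5.0 gives no denominator. Section 4.2 does name a population: "All subjects who are consented and enrolled into the clinical study will constitute the intention-to-treat (ITT) population for the purposes of adverse event reporting". The only other set in that section is narrower than the exposed subjects: "Only subjects implanted with the CI532 and fit with the CP1000/N7 Sound Processor and completed per the protocol will be considered as the completed cases". No set in the SAP consists of all subjects who underwent the procedure.

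Section 5.0 ends by planning a qualitative comparison of the rates with earlier cochlear implant studies, without a formal test.

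**The concern.** An exact binomial interval treats the count as a sum of independent yes/no outcomes, one per subject. An event total is a different quantity. One person can have nausea, then vertigo, then a wound problem, and all three are counted. The total then varies more than the binomial model allows, and it can exceed the number of subjects. The broad definition, which takes in minor symptoms and anesthesia effects regardless of relation to the device, makes several events per person plausible.

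The second part concerns who is counted. An enrolled subject who never comes to surgery cannot, under the section 5.0 definition, contribute an event, but belongs to the section 4.2 population. If that population is the denominator, such subjects lower the rate.

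The rates and their limits are the only safety summary this SAP plans, and they are to be set beside other studies' figures. A reader of that comparison needs to know whether a percentage means events or people, and out of whom.

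**Working it through.** **The plan's own figure.** There is none. The SAP gives no adverse event rate, expected count or number of subjects not implanted. The one input taken from it is the size: "A sample size of 100 adult subjects will be enrolled in the clinical investigation" (section 4.1). All event rates and numbers unexposed below are assumptions.

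**1. Why recurrence breaks the limits.** Let μ be the mean number of events per subject and N = 100. The binomial model gives the total a variance of Nμ(1 − μ). If events recur at random (Poisson), the variance is Nμ. If they also cluster in some subjects (negative binomial, shape k), it is N(μ + μ²/k). At μ = 0.6:

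- binomial: 100 × 0.6 × 0.4 = 24, SD 4.90
- Poisson: 60, SD 7.75
- clustered, k = 0.5: 60 + 100 × 0.36/0.5 = 132, SD 11.49

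The assumed SD is 4.90/7.75 = 63% or 4.90/11.49 = 43% of the true one, so the interval is too short.

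**2. Coverage.** With L(x) and U(x) the Clopper-Pearson 95% limits for x out of 100, coverage is the sum of P(X = x) over all x ≤ 100 for which L(x) ≤ μ ≤ U(x). Totals above 100 count as failures.

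| Events per subject (assumed) | Poisson | k = 1 | k = 0.5 |
|---|---|---|---|
| 0.05 | 98% | 98% | 97% |
| 0.1 | 94% | 93% | 92% |
| 0.3 | 92% | 87% | 83% |
| 0.6 | 80% | 69% | 62% |

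Heavier clustering (k = 0.3) gives 78% at 0.3 and 55% at 0.6. At 1.2 events per subject with k = 1, the total exceeds 100 in 89% of trials and no interval exists. At 0.05 to 0.1 events per subject, as a single uncommon event type might have, coverage stays near nominal.

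**3. One concrete row.** For 40 events in 100 subjects, the binomial limits are 30.3 to 50.3 per 100 subjects (width 20.0). Exact Poisson limits for the same count are 28.6 to 54.5 (width 25.9), before any allowance for clustering.

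**4. Dilution.** With a affected subjects and u never exposed, the reported rate is a/N and the exposed rate is a/(N − u). Their ratio is 1 − u/N. With a = 10 and N = 100:

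| Never exposed (assumed) | Rate among exposed | 95% exact limits |
|---|---|---|
| 0 | 10/100 = 10.0% | 4.9 to 17.6 |
| 5 | 10/95 = 10.5% | 5.2 to 18.5 |
| 8 | 10/92 = 10.9% | 5.3 to 19.1 |
| 20 | 10/80 = 12.5% | 6.2 to 21.8 |

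The plan's denominator would report 10.0% in every row.

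**The case against.** The best defence is that section 5.0 is loosely worded but means the right thing. Exact binomial limits exist only for a proportion of subjects, so a programmer might take frequency to mean subject incidence and leave recurrence to the patient-time rate in the same sentence. That reading is possible, but the text does not state it. The sentence names events, the counting rule takes in all of them, and where the SAP wants shares of individual subjects (the individual analyses in 4.3.2, the questionnaires in 4.5.5) it says so. The patient-time rate has no interval method of its own and leaves the binomial sentence standing.

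The denominator is also inferred by joining sections 4.2 and 5.0. Section 4.2 may only fix whose events are collected, and section 2.0 expects implantation: "Subjects in this study will be implanted with the commercially available Nucleus CI532 cochlear implant". This stands as a limit on the point. If everyone enrolled is operated on, there is no dilution, and at 8 of 100 the change is small beside the width of the limits. It is still the only adverse event population the SAP names.

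A reader might go further and infer that both the rates and their limits are simply wrong. The document does not support that. If no subject has more than one event in a row of the table, events equal subjects and the limits are valid. Nor would it be fair to set 30 events in 100 subjects (30%) against 15 affected subjects (15%) as the size of an error: these are two different quantities. The contrast shows only why the label matters.

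Finally, no safety hypothesis or stopping rule in the SAP depends on these limits, and the efficacy tests are untouched. That is correct and lowers the severity.

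**Conclusion.** The point holds conditionally. Followed literally, sections 4.2 and 5.0 give limits that are too narrow for overall and common-event rows when events recur: about 62 to 92% coverage at 0.3 to 0.6 events per subject, over the range from no clustering to k = 0.5. They give no limits at all when events outnumber subjects. Rare event types are little affected. The rate is diluted in proportion to the enrolled subjects never exposed, a share the SAP does not give and which may be zero; this is probably the smaller of the two effects.

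The coverage figures rest on assumed event rates and an assumed clustering model, with N = 100. The protocol was not available for this check; if it defines a safety denominator, section 5.0 should cite it.

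This should be fixed before the safety tables are produced. Because the rates are compared only qualitatively, it is not a critical defect.

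**What to change.** Amend sections 4.2 and 5.0 as follows:

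- Define a safety set: all subjects in whom implant surgery was started. This keeps attempted implantations at risk and leaves out those who never reached surgery.
- Give exact binomial limits only for the proportion of the safety set with at least one event: overall, serious, device-related, and by event type. Label it as subjects.
- Show event totals beside it without binomial limits, and use them for the patient-time rate. Count time from surgery and give Poisson limits, or limits robust to overdispersion where subjects have several events.
- List any events in enrolled subjects before surgery separately. This also settles how the instruction to count events whatever their onset fits a definition that requires exposure.

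The cost is SAP wording and table shells; no new data are needed. Reported figures may move in either direction: removing unexposed subjects raises a rate, and counting people in place of recurrent events lowers a percentage.

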9.0 Amendment to Protocol

The original CIP was amended to include two additional study visits.

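### The adverse event rate per patient-time mixes one-off surgical events with later ones, so it falls as follow-up lengthens and is not comparable with earlier studies of different length

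*SAP*

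**What the plan says.** SAP section 5.0 counts every event: "Adverse events will be counted regardless of severity, seriousness, onset, duration, or relation to study treatment". It recognises that events "may be associated with the implant procedure, including those from general anesthesia, or specifically associated with the use of the device".

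Two summary measures follow in one sentence. The first: "All adverse event rates will be reported as the number and frequency of events with corresponding 95% exact binomial confidence limits". The second is added to it: "as well as the number of events per patient-time (e.g., events per 10 patient years".

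Both are then set against outside data: "These values will be qualitatively compared to the same rates observed in previous cochlear implant studies; no formal statistical comparisons will be conducted".

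The section does not separate events around the operation from later ones. It sets no common follow-up window and does not ask that the earlier studies have similar follow-up. It also does not define the patient-time denominator. Section 4.2 takes all consented and enrolled subjects as the population for adverse event reporting.

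**The concern.** A rate per patient-year summarises risk well when the hazard is roughly constant. Two studies can be compared on it when that holds, or when their follow-up is equal. The SAP requires neither, and by naming procedure and anaesthesia events it makes a constant hazard implausible. Those events can arise only in a short period around a single operation. Each later month adds to the denominator and cannot add to that part of the numerator.

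If surgical risk is the same in two studies, the one with longer follow-up therefore shows the lower patient-time rate and looks safer. The bias can favour this trial or count against it, depending on how long the earlier studies ran. The comparison is the only external safety benchmark in the SAP. Because it is made by eye, a difference that comes only from duration could be read as a difference in safety.

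**Working it through.** The SAP states no adverse event rate, no event count and no follow-up for the earlier studies, so there is no figure of its own to reproduce. What follows is an illustration.

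**Inputs**
- From the SAP: 100 subjects (section 4.1); scheduled intervals up to 12 months after activation (section 4.5.3).
- Assumed: *p* = 0.1 to 0.3 perioperative events per subject; *l* = 0.05 to 0.1 later events per patient-year; follow-up *T* of 6, 13 and 24 months. The 13 months for this trial is also an assumption: 12 months plus about one month from surgery to activation. The SAP does not state the adverse event follow-up period.

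**Formula**

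Rate per 10 patient-years = 10 × (*p* + *l*·*T*)/*T* = 10 × (*p*/*T* + *l*)

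Only the first term depends on follow-up, and it shrinks as *T* grows. With *p* = 0.2 and *l* = 0.05:
- *T* = 0.5: 10 × (0.4 + 0.05) = 4.5
- *T* = 13/12: 10 × (0.1846 + 0.05) = 2.35
- *T* = 2: 10 × (0.1 + 0.05) = 1.5

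**Full grid (rate per 10 patient-years)**

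| *p* | *l* | 6 months | 13 months | 24 months | 6 vs 13 | 24 vs 13 |
|---|---|---|---|---|---|---|
| 0.1 | 0.05 | 2.5 | 1.42 | 1.0 | 1.76 | 0.70 |
| 0.1 | 0.10 | 3.0 | 1.92 | 1.5 | 1.56 | 0.78 |
| 0.2 | 0.05 | 4.5 | 2.35 | 1.5 | 1.92 | 0.64 |
| 0.2 | 0.10 | 5.0 | 2.85 | 2.0 | 1.76 | 0.70 |
| 0.3 | 0.05 | 6.5 | 3.27 | 2.0 | 1.99 | 0.61 |
| 0.3 | 0.10 | 7.0 | 3.77 | 2.5 | 1.86 | 0.66 |

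The ratios run from 1.56 to 1.99 at 6 months and from 0.61 to 0.78 at 24 months. Risk per implantation is the same across each row.

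**Second set of assumptions.** Take 100 subjects, 5 to 20 perioperative events in total, 0 to 0.10 later events per patient-year, and follow-up of 0.5, 1 or 2 years. With 10 perioperative events and no later ones, the rate is 10 × 10/50 = 2.0, 10 × 10/100 = 1.0 and 10 × 10/200 = 0.5. Over the whole set, the half-year rate is 1.33 to 2.0 times the one-year rate and 1.6 to 4.0 times the two-year rate.

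**The frequency measure.** For perioperative events alone it does not move: 10 events in 100 subjects, each in a different subject, is 10% (exact 95% limits 4.9% to 17.6%) at any follow-up. For all events together it rises. With *p* = 0.2 and *l* = 0.05, *p* + *l*·*T* is 0.225 events per subject at 6 months, 0.254 at 13 and 0.30 at 24.

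**After a split by risk window.** The perioperative figure stays at 10%. The later rate is 10 × *l*, or 0.5 per 10 patient-years for *l* = 0.05, whatever the follow-up.

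**The case against.** The strongest reply is that this touches one of two descriptive measures. The frequency with exact limits stands first in the same sentence and is compared too. A reader who sees the frequency rise and the patient-time rate fall can suspect an effect of duration. The comparison is qualitative, the SAP has no safety threshold or success criterion, and its formal hypotheses concern efficacy. Distortion also needs earlier studies of different length, which the SAP does not describe, and the protocol may define the adverse event period. All of this stands and limits the weight of the point. It does not repair the patient-time figure, which is compared in its own right.

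Three stronger readings are tempting, and the document does not support them.

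- A reader might infer that the whole safety comparison reflects study duration. It does not, because the frequency of perioperative events is unaffected.
- A reader might infer that only one pooled rate will be shown. Section 5.0 speaks of rates in the plural and defines device-related and serious events. Counting events whatever their onset or relation is a rule of inclusion and does not bar rates by type. What is missing is a split by time since surgery.
- A reader might infer that the amendment dilutes the rate further. Section 9.0 says only: "The original CIP was amended to include two additional study visits". The SAP does not say when these visits occur or that their time enters the denominator of section 5.0, so no such effect can be calculated.

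**Conclusion.** The point holds for the patient-time measure. As planned, it puts one-off surgical and anaesthetic events over follow-up time, so it depends on study length and cannot be compared between studies that differ in it. The grid puts the distortion at up to about two-fold against a 6-month study and about 40% against a 24-month one. Those figures rest wholly on assumed event rates and follow-up lengths, including the 13 months for this trial. If follow-up happens to match that of the earlier studies, there is no distortion.

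Severity is minor: a sound measure for perioperative events is reported alongside, and no test or decision rule uses the comparison. It is a cheap improvement worth making.

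**What to change.** In SAP section 5.0:

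- Report events from surgery to a fixed early cut (for example, initial activation) per implanted subject, with exact binomial limits on the proportion of implanted subjects affected. Name this denominator, since section 4.2 takes all enrolled subjects.
- Report events after the cut per patient-time, counted from the cut to last contact.
- Compare each figure with earlier studies only over a matched window, or show the follow-up length of both studies beside it.

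The cost is a few lines of SAP text and one extra table built from event onset dates. Some earlier studies may not report events by window, so fewer will be available for comparison.

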6.0 Justification of Pooling Across Study Sites

Pooling data from study sites will be done based on the following: all sites will have the same protocol, the sponsor will monitor the sites to assure protocol compliance, and the data gathering mechanism (case report forms and data acquisition) will be the same across all study sites (Meinert, 1986).

Consistency of the primary efficacy endpoints between sites will be assessed by testing for a difference between sites in the change in CNC word score from preoperative to 6 months postoperative via an analysis of variance model, with the change in CNC word score as the outcome and site as the factor. A p-value for the site factor of less than 0.10 will be considered evidence of differences between sites for the primary efficacy outcome. If there is evidence of a difference, additional analyses will be performed to explore the possible role of baseline characteristics to explain the results. Results for the primary efficacy endpoint will also be presented separately by site, irrespective of the test of differences between sites to help understand both qualitative and non-significant differences between sites

7.0 Missing Data

All efforts will be put forth to ensure near complete follow-up, with particular focus on the assessment of the primary outcome and occurrence of adverse events. A reminder of subject follow-up due date will be provided to participating centers to facilitate scheduling of the follow-up visit.

In the event a subject is withdrawn prior to the 6-month assessment, the subject will be noted as withdrawn and data collected to the time of withdrawal will be reported. In publication and presentation information and data on the withdrawn subjects will be discussed but not included in the final cohort that reached 6 months.

8.0 Reporting of Results

Results of the analyses outlined in this statistical analysis plan will be reported their entirety in planned publication(s) following the completion of endpoint data collection of all 100 subjects.

9.0 Amendment to Protocol

The original CIP was amended to include two additional study visits.

9.1 Primary Purpose

The primary purpose of these visits is to evaluate whether a change in cochlear implant programming, specifically an increase in the number of channels (maxima) will improve subject speech perception in quiet and noise.

9.2 Primary Effectiveness Endpoint Analysis

Phase 2 CNC Endpoint

Although the stated objective implies a statistical hypothesis test that the paired difference in CNC scores for 16 Maxima MAP compared to 8 Maxima MAP is different from 0, a test of non-inferiority will be stated.

The endpoint will compare CNC scores following 16 maxima MAP compared to the original programming and will be evaluated with a paired t-test. Formally the hypothesis is:

$$H_0: \mu_d \leq -M$$

$$H_a: \mu_d > -M$$

where μ_d is the mean of the paired difference in 16 maxima MAP (new device programming) CNC from 8 maxima MAP (original device programming) CNC and M represents the non-inferiority margin of 10%.

Non-inferiority Design:

All sample size assumptions performed in PASS2020.

Key Sample Size Assumptions:

- Paired t-Test for Non-inferiority
- Mean of paired differences = 0 (*i.e. assuming no difference in average CNC score for both programming*)
- No adjustment for attrition

In Table 1 below, sample sizes are presented under varying assumptions. The first column, “Non-Inferiority Margin” represents the magnitude of the margin of the non-inferiority for the mean of paired differences. For this study, higher mean values indicate a “better” response. The value “-10” is the distance below zero for which the new (16 maxima MAP) will still be considered non-inferior to the original MAP. In the FOX study Group 2, MAPs were compared in a group of existing CI users for which the SD was 10%. The estimated standard deviation for the 6 month primary endpoint (Change in CNC at 6 months) sample size calculations was 22.4%. The sample size estimations are presented for both possibilities to provide a range of requirements should the SD be higher than that observed in the FOX study.

Sample size requirements are provided for both 80% and 90% power. Additionally, sample estimates are presented for both a one-sided alpha=0.05 and one-sided alpha = 0.025.

The minimum sample size to maintain 90% power with a standard deviation of 10% is 13 subjects. Other options are provided below in Table 1.

Table 1.
Sample size calculations for Pair T-test of Non-Inferiority

Power	Assumptions		Total Sample Size Requirements	
	Non-Inferiority Margin	Standard Deviation	Minimum Sample Size One-sided Alpha = 0.025	Minimum Sample Size One-sided Alpha = 0.050
80%	-10.0	10.0%	10	8
	-10.0	22.4%	42	33
90%	-10.0	10.0%	13	11
	-10.0	22.4%	55	45

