9.2 Additional Analyses

- Evaluation of the effect of performance in Quiet and Noise with Wrapping Factor (measure of modiolar proximity)
- Evaluation of the score obtained on the ACE-27 with speech perception outcomes (both original MAP and 16 maxima MAP)
- Observation of TIM measurements and data obtained from a 3D reconstruction of a CT scan.
- Observation of sound quality ratings for the original MAP and 16 maxima in both quiet and noise

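### The added-visits phase asks whether 16 maxima improves speech perception in quiet and noise, but its only formal test is CNC non-inferiority with a 10-point margin, and the SAP states no 16-versus-8 comparison of speech in noise

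*SAP*

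**What the plan says.** SAP section 9.1 states that the visits added by amendment are to evaluate whether "an increase in the number of channels (maxima) will improve subject speech perception in quiet and noise".

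Section 9.2, Primary Effectiveness Endpoint Analysis, then sets the analysis:

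- It acknowledges that the objective implies a test of whether the paired CNC difference "is different from 0, a test of non-inferiority will be stated".
- On the comparison: "The endpoint will compare CNC scores following 16 maxima MAP compared to the original programming and will be evaluated with a paired t-test". The null hypothesis is that the mean difference, 16 minus 8 maxima, is at or below -M.
- On the margin: "M represents the non-inferiority margin of 10" per cent. The value -10 "is the distance below zero for which the new (16 maxima MAP) will still be considered non-inferior to the original MAP".
- The true difference is assumed to be 0. The SD is 10 (from an earlier comparison of MAPs in existing users) or 22.4 (from the main study's sample size calculation).
- On the test level: "sample estimates are presented for both a one-sided alpha=0.05 and one-sided alpha = 0.025". The headline minimum is 13 subjects for 90% power at SD 10.

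Noise appears only under the second heading numbered 9.2, Additional Analyses. One item there is "Evaluation of the effect of performance in Quiet and Noise with Wrapping Factor". Another relates the ACE-27 score to speech perception outcomes under both MAPs. A third observes sound quality ratings for both MAPs in quiet and in noise.

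**The concern.** The purpose is directional: does the new programming improve perception? The test asks whether it is worse by as much as 10 points. Rejecting the stated null hypothesis leaves a small loss, no change and a gain all possible. The plan names the mismatch but gives no reason for the switch, no justification of the margin and no superiority step to follow.

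The purpose also names noise. The one formal test uses CNC words, which the SAP treats as a measure in quiet (sections 4.1 and 4.3.1). No analysis in the SAP compares speech-in-noise scores between the two MAPs.

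If the plan is followed exactly, the added phase can meet its endpoint without answering its question. A reader who takes the purpose from section 9.1 and the result from section 9.2 could conclude that 16 maxima improves perception when no such test was made.

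**Working it through.** **Inputs.** All are from section 9.2, Primary Effectiveness Endpoint Analysis: margin M = 10, read as percentage points of CNC score; assumed true difference 0; SD of the paired difference 10 or 22.4; power 80% or 90%; one-sided alpha 0.025 or 0.05; paired t-test.

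**Step 1: reproduce the plan's figures.** For a true mean difference d, the power of the paired non-inferiority test is P(T > t[1-alpha, n-1]), where T is noncentral t with n-1 degrees of freedom and noncentrality (d + M)√n/SD. The smallest n reaching the target power with d = 0 is:

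| Power | SD | alpha 0.025 | alpha 0.05 |
|---|---|---|---|
| 80% | 10 | 10 | 8 |
| 80% | 22.4 | 42 | 33 |
| 90% | 10 | 13 | 11 |
| 90% | 22.4 | 55 | 45 |

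All eight cells agree with Table 1, so the arithmetic is sound. The headline n = 13 is the one-sided 0.025 cell; the 0.05 cell is 11.

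**Step 2: observed loss that still meets the endpoint.** Non-inferiority is declared when the observed mean difference exceeds -M + t[1-alpha, n-1]·SD/√n. At one-sided 0.025 and 90% power:

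- n = 13, SD 10: the half-width is 6.04, so the limit is -10 + 6.04 = -3.96.
- n = 55, SD 22.4: the half-width is 6.06, so the limit is -3.94.

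**Step 3: chance of meeting the endpoint when 16 maxima truly lowers CNC** (same formula, d < 0, one-sided 0.025):

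| True difference | n = 13, SD 10 | n = 55, SD 22.4 |
|---|---|---|
| 0 | 91% | 90% |
| -2 | 75% | 74% |
| -3 | 64% | 62% |
| -5 | 38% | 37% |

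**Step 4: what a superiority test would deliver.** Replace the noncentrality with d√n/SD and test H0: mean difference ≤ 0 at one-sided 0.025. The SAP gives no target gain for this phase, so a range is assumed.

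| True gain | Power, n = 13, SD 10 | n for 90%, SD 10 | n for 90%, SD 22.4 |
|---|---|---|---|
| 3 | 17% | 119 | 588 |
| 5 | 38% | 44 | 213 |
| 10 | 91% | 13 | 55 |

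The last row equals the plan's own sample sizes because a 10-point gain tested against 0 is as far from its null value as a zero difference is from -10.

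**Step 5: noise.** Set section 9.1 beside the four items under Additional Analyses. One relates performance in quiet and noise to wrapping factor; one relates ACE-27 to speech outcomes under both MAPs; one sets TIM measurements beside CT data; one observes sound quality ratings under both MAPs. None is a 16-versus-8 comparison of speech-in-noise scores.

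**The case against.** The strongest reply is that the choice is open and deliberate. The plan admits that the objective implies a different test, the revision history records a change to the hypothesis testing, and hypothesis, margin and sample sizes agree with one another. Nowhere does it say that meeting non-inferiority demonstrates improvement. Some tolerated loss is inherent in any non-inferiority test, and a gain could be read from the same paired confidence interval. The phase is a within-subject add-on and leaves the main study's endpoints untouched. All of this stands. It does not make the test answer the purpose, and the plan neither specifies that interval for this phase nor ties a claim of improvement to it.

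Several stronger readings are tempting and are not supported:

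- **That the phase sets out to show improvement.** Section 9.1 says it will evaluate whether there is one.
- **That noise is ignored.** Sound quality ratings in noise are observed under both MAPs. What the SAP lacks is a comparison of speech-in-noise scores. The amended protocol is not at hand and may list one.
- **That losses of 7 or 8 points would pass.** At SD 10 the limit is -7.30 for n = 55 and -8.02 for n = 100. But Table 1 ties 55 to SD 22.4, and 100 is the main-study enrolment. With n = 13 and SD 10 at 0.025, a significant loss (below -6.04) cannot pass.
- **That alpha is left to be chosen later.** No sentence fixes it for this phase, and at n = 13 the 0.05 level would move the limit from -3.96 to -5.06. But the headline 13 belongs to 0.025, the level used for the main study's tests. This is a small omission.
- **That the noise data are already in hand.** The SAP does not say so.

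**Conclusion.** The point holds as a mismatch between purpose and test. The only formal test supports a statement that 16 maxima is not worse than 8 by 10 points or more on CNC words, and can be met with an observed mean loss of up to about 4 points at the plan's own 90%-power, 0.025 designs. It cannot support a statement that 16 maxima improves perception, and the noise part of the purpose has no between-MAP comparison of speech scores in the SAP. The sample size calculation itself is correct.

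This rests on the margin being in percentage points and on an observed SD near one of the two planned values. The gains and losses used in the power figures are illustrative.

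**What to change.** 1. Keep non-inferiority of CNC as step 1 and state its level as one-sided 0.025.
2. If step 1 is met, test superiority (H0: mean difference ≤ 0) on the same paired CNC differences at one-sided 0.025. The fixed order means that this costs no alpha.
3. Where speech in noise is measured under both MAPs, test the paired 16-versus-8 difference next in the sequence at the same level. Otherwise, limit the purpose in section 9.1 to CNC in quiet.
4. State that non-inferiority alone does not support a claim of improvement.
5. Report superiority power at the actual n. At n = 13 and SD 10 it is 38% for a true 5-point gain and 91% for 10 points; 90% power at 5 points needs 44 subjects.

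The cost is SAP wording and up to two further paired tests. There are three drawbacks. The modest superiority power has to be shown openly. In a fixed sequence, the noise test is formal only if CNC superiority is met. The added tests must be specified before the data from these visits are examined, or else labelled post hoc.
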